hematuria, proctitis, or fistula are not observed. If 2 additional subjects are enrolled at 60 Gy, we will review for DLTs after completion of the 90 day DLT window and enroll 3 additional subjects at 60 Gy if DLT has been observed in 1 subject, or enroll 1 subject at 75 Gy if no DLT were observed or terminate the trial if $\geq 33\%$ DLT were observed in all subjects. For the next group of subjects at 60 Gy, we will review DLT/toxicity after all three subjects have completed the 90 days DLT window after EBRT. After the first subject's DLT window is complete (90 days post-EBRT) at 75 Gy, we will make a decision to enroll additional subjects at 75 Gy only if Grade 4-5 hematuria, proctitis, or fistula are not observed. If 2 additional subjects are enrolled at 75 Gy, we will review for DLTs after completion of the 90 day DLT window and enroll 3 additional subjects at 75 Gy if DLT has been observed in 1 subject, or terminate the trial if $\geq 33\%$ DLT were observed among the first three subjects at 75 Gy. For the next group of three subjects at 75 Gy, we will review DLT/toxicity after all three subjects have completed the 90 days DLT window. We will additionally describe rates of complications and toxicity (i.e., acute and late overall, GU and GI) by grade and by dose once the 6 month follow-up period is complete for all subjects. Toxicities among those not receiving EBRT will not affect the MTD determination or the decision to enroll additional patients at the same dose or at a higher dose. The DMC will review data at least once annually.

If the DMC recommends termination of the study we will terminate the study. If in the first subject at any dose Grade 4-5 hematuria, proctitis or fistula occur, we will terminate the study. If $\geq 33\%$ of subjects experience DLT (i.e., Grade 3 hematuria, proctitis, urinary retention) within the first 90 days post EBRT, the trial will be closed.

The Clavien-dindo classification of surgical complications will be used to assess complications and the NCI-CTCAE v4.0 in addition to the RTOG acute and late morbidity scoring criteria will be used to grade adverse events and toxicity.

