Should a temporary or permanent suspension of our study occur, we will report the occurrence to the IRB and CivaTech Oncology®. If terminated, we will inform the IRB and research offices of termination. If terminated, we will continue to offer the standard of care for study subjects. If study termination is due to safety concerns, we will inform subjects by phone, mail or email of the study's status. If terminate not due to safety concerns, we will inform subjects during routine clinical visits.

The study will use the DSMC of the TCI as the data monitoring committee. All unexpected adverse events will be presented to the DSMB for review. All recommendations of the DSMB will be followed and implemented. If a situation arises in which the DSMC recommends termination of the study, we will terminate the study. To ensure data accuracy and completeness, random checks will be done by members of the search team listed in the protocol who are not directly responsible for data collection

[Type here]

Protocol Title:	A Phase I Single-Arm Open Label Dose-Escalation Study of CivaSheet with Radical Prostatectomy with or without Adjuvant External Beam Radiation Therapy in Patients with High Risk Prostate Cancer
Principal Investigator Name/Contact Info:	[name]/ [contact]/ [contact]
Primary Contact Name/Contact Info	[contact] [name]
Date Revised:	7/22/2022
Study Number:	GCO#1: 16-1314

and entry. Data irregularities and errors will be collected and reported to the PI. Should a temporary or permanent suspension of our study occur, we will report the occurrence to the IRB and MiMedx®. This study will use of the Tisch Cancer Center as the data monitoring committee. If notable safety issues are found in our interim analysis, the study will be interrupted as per DSMB recommendations. DSMB recommendations will be followed and implemented.

Study documentation includes all Case Report Forms, data correction forms or queries, source documents, Sponsor-Investigator correspondence, monitoring logs/letters, and regulatory documents (e.g., protocol and amendments, IRB correspondence and approval, signed subject consent forms).

Source documents include all recordings of observations or notations of clinical activities and all reports and records necessary for the evaluation and reconstruction of the clinical research study.

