[Type here]

Protocol Title:	A Phase I Single-Arm Open Label Dose-Escalation Study of CivaSheet with Radical Prostatectomy with or without Adjuvant External Beam Radiation Therapy in Patients with High Risk Prostate Cancer
Principal Investigator Name/Contact Info:	[name]/ [contact]/ [contact]
Primary Contact Name/Contact Info	[contact] [name]
Date Revised:	7/22/2022
Study Number:	GCO#1: 16-1314

- Unrelated – The AE is clearly NOT related to the study treatment.

Note: This includes all events that occur within 30 days of the last dose of protocol treatment. Any event that occurs more than 30 days after the last dose of treatment and is attributed (possibly, probably, or definitely) to the agent(s) will also be reported accordingly.

Step 4: Determine the prior experience of the adverse event.

Expected events are those that have been previously identified as resulting from administration of the agent. An adverse event is considered unexpected, for expedited reporting purposes only, when either the type of event or the severity of the event is not listed in:

- the current known adverse events listed in the Agent Information Section of this protocol;
- the drug package insert;
- the current Investigator's Brochure

- Reporting Requirements for Adverse Events

Expedited Reporting

- The Principal Investigator will be notified within 24 hours of learning of any serious adverse events, regardless of attribution, occurring during the study or within 30 days of the last administration of EBRT.
- Expedited reporting to Civatech Oncology is not required for adverse events.
- The IRB/PPHS will be notified within 5 business days of “any unanticipated problems involving risk to subjects or others” (UPR/UPIRSO).

- The following events meet the definition of UPR

- a. Any new information that indicates a new or increased risk, or safety issue (e.g., interim analysis, safety monitoring report, publication, updated sponsor safety report), that indicates an unexpected change to the risk/benefit ratio for the research.

[Type here]

Protocol Title:	A Phase I Single-Arm Open Label Dose-Escalation Study of CivaSheet with Radical Prostatectomy with or without Adjuvant External Beam Radiation Therapy in Patients with High Risk Prostate Cancer
Principal Investigator Name/Contact Info:	[name]/ [contact]/ [contact]
Primary Contact Name/Contact Info	[contact] [name]
Date Revised:	7/22/2022
Study Number:	GCO#1: 16-1314

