- b. An investigator brochure, package insert, or device labeling is revised to indicate an increase or magnitude of a previously known risk, or describes a new risk.
- c. Withdrawal, restriction, or modification of a marketed approval of a drug, device, or biologic used in research protocol
- d. Protocol deviation or violation that harmed subjects or others or that indicated subjects or others might be at increased risk of harm.
- e. Complaint of subject that indicates subjects or others might be at increased risk of harm or at risk of a new harm
- f. Any breach in confidentiality that may involve risk to the subject or others.
- g. Any harm experienced by a subject or other individual that in the opinion of the investigator is unexpected and at least probably related to the research procedures.

- Routine Reporting

All other adverse events- such as those that are expected, or are unlikely or definitely not related to the study participation- are to be reported annually as part of regular data submission.

- Stopping Rules

If the DMC recommends termination of the study we will terminate the study. If in the first subject at any dose Grade 4-5 hematuria, proctitis or fistula occur, we will terminate the study. If $\geq 33\%$ of subjects experience DLT at any dose level (i.e., Grade 3 hematuria, proctitis, urinary retention) within the first 90 days post EBRT, the trial will be closed.

- In accordance with local IRB requirements, the following information will be reported within five (5) business days.
 - Non-compliance with federal regulations governing human research or with the requirements or determinations of the IRB, or an allegation of such non-compliance
 - Failure to follow the protocol due to the action or inaction of the investigator or research staff.

[Type here]

Protocol Title:	A Phase I Single-Arm Open Label Dose-Escalation Study of CivaSheet with Radical Prostatectomy with or without Adjuvant External Beam Radiation Therapy in Patients with High Risk Prostate Cancer
Principal Investigator Name/Contact Info:	[name]/ [contact]/ [contact]
Primary Contact Name/Contact Info	[contact] [name]
Date Revised:	7/22/2022
Study Number:	GCO#1: 16-1314

- Breach of confidentiality
- Premature suspension or termination of the research by the sponsor or investigator.

g) Withdrawal of Subjects:

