3. Justify your choice of principal monitor in terms of the assessed risk to the research subject's health and wellbeing. In high risk studies when the principal monitor is independent of the study staff, indicate the individual's credentials, relationship to the PI, and the rationale for selection.
4. List the specific items that will be monitored for safety (e.g., adverse events, subject compliance with the protocol, drop outs, etc.).
5. Indicate the frequency at which ACCUMULATED safety and data information (items listed in number 3 above and interim analysis of efficacy outcomes) will be reviewed by the monitor(s) or the Data Monitoring Committee (DMC). Although this information must be reviewed at least annually, the higher the study risks, the more frequently reviews must be scheduled.
6. Where applicable, describe rules which will guide interruption or alteration of the study design.
7. Where applicable, indicate dose selection procedures that will be used to minimize toxicity.
8. List any specialized grading system that will be used to evaluate adverse events (e.g., National Cancer Institute Common Toxicity Criteria).
9. Describe procedures that will be used to assure data accuracy and completeness.
10. Should a temporary or permanent suspension of your study occur, in addition to the PPHS, indicate to whom (NIH, FDA, sponsor, IRB) will you report the occurrence.

j) Withdrawal of Subjects:

[Type here]

Protocol Title:	A Phase I Single-Arm Open Label Dose-Escalation Study of CivaSheet with Radical Prostatectomy with or without Adjuvant External Beam Radiation Therapy in Patients with High Risk Prostate Cancer
Principal Investigator Name/Contact Info:	[name]/ [contact]/ [contact]
Primary Contact Name/Contact Info	[contact] [name]
Date Revised:	7/22/2022
Study Number:	GCO#1: 16-1314

Subjects can be taken off the study treatment and/or study at any time at their own request, or they may be withdrawn at the discretion of the investigator for safety, behavioral or administrative reasons without the subject's consent. The reason for study removal and the date the subject was removed will be documented in the Case Report Form. The subject will be followed-up per protocol unless subject voluntarily withdraws consent from study. Reasons for discontinuation may include:

- Subject voluntarily withdraws from treatment (follow-up permitted);
- Subject withdraws consent (termination of treatment and follow-up);

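### No DMC review of cohort DLT data is required before 75 Gy opens, and a DLT classed as expected has no assured prompt route to the committee

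*Protocol*

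**What the plan says.** **Who decides.** The Protocol's monitoring text (Section 3, before the Adverse Events heading) has the study team review DLTs after each group's 90-day window. The team then decides whether to enrol more men, move to 75 Gy or stop. Section 3(c) sets out the same sequence and gives the committee no part in it.

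**What the committee is assured.** It is called DMC, DSMC and DSMB in different places and is the cancer institute's existing committee. Its recommendations, including termination, are binding. Its scheduled contact is: "The DMC will review data at least once annually". Its event-driven contact is: "All unexpected adverse events will be presented to the DSMB for review". One further sentence reads: "If notable safety issues are found in our interim analysis, the study will be interrupted as per DSMB recommendations". No timing, trigger or content is given for that interim analysis.

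**Other routes.** Under Routine Reporting, remaining events, including expected ones, "are to be reported annually as part of regular data submission". Under Expedited Reporting, "The Principal Investigator will be notified within 24 hours of learning of any serious adverse events"; that notice goes to the investigator. The IRB has a five-business-day route for unanticipated problems only.

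**What a DLT is.** The SAP's primary outcome counts Grade 3 or higher urinary retention, hematuria or rectal bleeding/proctitis within 90 days after EBRT.

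**The concern.** In a dose-escalation trial, the decision that most needs an outside look is the opening of the higher dose. Here the committee can stop the study, but nothing ensures that it holds the relevant data when that decision is made. Between annual reviews it is sent unexpected events. Hematuria and radiation proctitis appear in the monitoring text as known effects of radiation, so a DLT of either kind may be classed as expected and left to annual reporting.

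The rules that the team applies alone are also not consistent. In the monitoring text, one DLT in three men leads to expansion at 60 Gy, yet 1/3 = 33.3% also meets the termination threshold of at least 33%. Section 3(c) and the monitoring text differ on whether three or six men must be observed before 75 Gy. Section 3(c) also gives both 30 and 90 days as the observation period. Those conflicts must be reconciled separately. Until they are, an independent look at the step has extra value.

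**Working it through.** The plan states no figure for this point, so the check is calendar arithmetic.

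**Inputs**
- Implant to start of EBRT: 6 weeks = 42 days. EBRT: 5 weeks = 35 days. DLT window: 90 days (SAP, primary outcome).
- Groups run in sequence as 1, then 2, then 3 men per dose (Protocol 3(c)).
- Monitoring text: 75 Gy may open after two groups (three men) with no DLT. Section 3(c): after three groups (six men).
- Maximum duration: 44 months for 12 men (Protocol 3(d)).
- Assumptions: reviews at the minimum frequency, on days 365 and 730 from first implant; men in a group implanted together; no replacements.

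**One group:** 42 + 35 + 90 = 167 days.

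**Pace implied by 44 months:** 44 × 30.4375 = 1,339 days. Six groups take 6 × 167 = 1,002 days. The remaining 337 days, spread evenly, give 337 / 6 ≈ 56 days per group, or 167 + 56 = 223 days from one group's start to the next.

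| Path | Accrual | 75 Gy opens | Completed windows at the last review before that | Not covered |
|---|---|---|---|---|
| Monitoring text, 0/3 DLT | no gaps | 2 × 167 = day 334 | no review yet | subjects 1-3 |
| Section 3(c) | no gaps | 3 × 167 = day 501 | day 365: subjects 1-3 (closed day 334) | subjects 4-6 |
| Monitoring text, 0/3 DLT | 56-day gaps | 2 × 223 = day 446 | day 365: subject 1 (closed day 167) | subjects 2-3 (closed 223 + 167 = day 390) |
| Section 3(c) | 56-day gaps | 3 × 223 = day 669 | day 365: subject 1 | subjects 2-3 and 4-6 (the latter closed 446 + 167 = day 613) |

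In the second row, subjects 4-6 are implanted on day 334. The day-365 review falls 365 − 334 = 31 days later, before their EBRT starts on day 42 after implant.

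If the 337 days are spread over the five intervals between groups instead, the gap is about 67 days. 75 Gy then opens at 2 × 234 = day 468 or 3 × 234 = day 702. Both still fall between the reviews on days 365 and 730, and subjects 2-3 (closed 234 + 167 = day 401) still miss the first.

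**The first man at 75 Gy.** The next two men can start on day 334 + 167 = 501, 501 + 167 = 668, 446 + 223 = 669 or 669 + 223 = 892, in the order of the table. In the first case the last review was on day 365, 31 days after his implant. In the second and third it was on day 365, before his implant. In the fourth it was on day 730, 730 − 669 = 61 days after his implant and during EBRT (days 42 to 77). In no case has his completed window been reviewed.

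**How often the deciding data would contain a DLT.** The Protocol expects a true risk of 10% to 50%. Take independent outcomes and set aside the first-subject Grade 4-5 rule. The chance of 0/3, which the day-334 path needs, is (1 − p)³: 0.73 at 10%, 0.34 at 30% and 0.13 at 50%. Under Section 3(c), escalation after six men allows at most one DLT (1/6 < 33%; 2/6 is not). The chance that 75 Gy opens with that one DLT among subjects 4-6 is 3p(1 − p)⁵: 0.18 at 10%, 0.20 at 20%, 0.15 at 30%, 0.09 at 40% and 0.05 at 50%.

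**The case against.** The case on the other side has weight.

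- **The annual review is a floor.** The committee may meet more often, and the unscheduled interim analysis may bring DLT data to it. A charter, which the form text in Section 3(h) mentions, is not in these documents and may set cohort reviews. This stands: the finding is about what the documents assure, not about what will happen.
- **The earliest opening has no DLT to report.** Day 334 requires 0/3 DLTs, the monitoring text's path and total accrual gaps of at most 365 − 334 = 31 days. This stands for that path. It does not answer Section 3(c), where 75 Gy can open with one DLT among men whose windows the committee has not seen.
- **Some DLTs may count as unexpected.** Step 4 of the expedited-reporting text makes an event unexpected if its type or its severity is not listed. The monitoring text lists hematuria and proctitis without grades and omits urinary retention. A severe event may therefore reach the committee promptly. That depends on source documents not supplied here, so the route is possible but not assured.
- **Other safeguards exist.** Stopping rules are prespecified, and a first subject at each dose completes his window before others enrol. The committee can act whenever it has cause, so a reader should not infer that it is powerless.

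Two further inferences are tempting but unsupported. One is that 24-hour SAE notice ends 30 days after EBRT, leaving the last 60 days of the DLT window uncovered. The text covers serious events "occurring during the study or within 30 days of the last administration of EBRT"; the two limbs are alternatives, and a note under Step 3 also has later treatment-attributed events reported. That notice goes to the investigator, so its end date would not delay the committee in any case. The other is that the plan breaches its own requirement that "the higher the study risks, the more frequently reviews must be scheduled". That is unfilled form text under Section 3(i), for other projects, and not a commitment of this trial.

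**Conclusion.** The point holds as a gap in assured oversight. The documents require no committee review of cohort DLT data before 75 Gy opens, and they give a DLT classed as expected no assured prompt route to the committee. On the minimum schedule, the deciding group's completed windows go unreviewed in all four scenarios: openings on days 334 and 501 without gaps, and about days 446 and 669 at the pace implied by 44 months. The first 75 Gy man's completed window also goes unreviewed before the next two men start.

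This rests on an annual clock starting at first implant, simultaneous implants within a group, no replacements, and 44 months meaning six sequential groups evenly spaced. Slower accrual changes which review comes first but does not ensure that it covers the deciding group. It would be wrong to say that no review ever precedes 75 Gy: in three of the four scenarios the day-365 review does, with incomplete data. This is a worthwhile, inexpensive improvement to the monitoring plan, not a flaw in the DLT definition or the analysis.

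**What to change.** In the Protocol's monitoring text:

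1. Before 75 Gy opens, and again before enrolment continues after the first 75 Gy subject, send the cumulative DLT table to the existing committee and record its reply.
2. Send every DLT and every Grade 4-5 event to the committee on occurrence, whether or not it is classed as expected.
3. Give the interim analysis a time and content, or say that it is the review in item 1. If a charter already provides for these reviews, cite it.

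Under Expedited Reporting, define when the study ends for the purpose of SAE notice, including for men who receive no EBRT. This is a clarification only.

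Separately, Section 3(c) and the monitoring text must be reconciled on when 75 Gy may open and on the observation period before it.

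The cost is two short committee reviews, event notices for at most 12 evaluable men, and a short delay at each of the two steps. The documents give no committee turnaround time, so the length of that delay is an assumption to settle with the committee. No new committee or patient procedure is needed.

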A Phase I Single-Arm Open Label Dose-Escalation Study of CivaSheet With Radical Prostatectomy With or Without Adjuvant External Beam Radiation Therapy in Patients With High Risk Prostate Cancer

[name]

NCT03657108

Document Date: 10-18-2022

**Primary Outcome:** We will determine the MTD for Civasheet when administered with RP and adjuvant EBRT. MTD is defined as the highest dose of the Civasheet® not yielding unacceptable toxicity. Specifically if > 33 % of subjects experience DLT at any dose level, the dose level below that level will be considered the MTD. Or if the highest level (75 Gy) has been reached and < 33% of subjects have experienced DLT, 75 Gy will be considered the MTD.. The present study defines dose limiting toxicity as the development of Grade 3 or higher (According to the NCI'S CTCAE v 4.0) urinary retention, hematuria or rectal bleeding/radiation proctitis within 90 days post EBRT which is given 6 weeks after RP + Civasheet implant for 5 weeks. Toxicities experienced among those not receiving adjuvant EBRT will not be used in the determination of the MTD. Binary or categorical outcomes will be described with proportion and 95% confidence intervals and continuous measures will be summarized with mean (SD) or median (IQR), as appropriate.

While all genitourinary and gastrointestinal toxicities according to the NCI-CTCAE will be documented and evaluated every time a subject is seen Grade 3-5 hematuria, urinary retention and rectal bleeding/radiation proctitis are the specific toxicities used for dose escalation procedures. This study defines DLT as the development of NCI-CTCAE Grade >3 urinary retention, Grade 3 hematuria or Grade 3 rectal bleeding/radiation proctitis within 90 days post EBRT which is given 6 weeks after RP + Civasheet implant for 5 weeks. Grade 3 hematuria according to the NCI-CTCAE is defined as gross hematuria with indications including transfusion, IV medications, hospitalization, elective endoscopic, radiologic or operative intervention and limiting self-care activities for daily living. Grade 3 urinary retention is defined as an incomplete ability to empty the bladder with indications including elective operation or radiologic intervention, substantial loss of affected kidney function or development of mass. Grade 3 rectal bleeding/proctitis is defined as severe symptoms; fecal urgency or stool incontinence and limiting self-care activities for daily living. If > 33% of subjects experience these DLT at any dose, the dose level below that level will be considered the MTD. If  $\geq 33\%$  subjects experience a DLT at 60 Gy, the trial will be closed and no additional subjects will be enrolled. Also, if the first subject enrolled at 60 Gy experiences NCI-CTCAE Grade 4 or higher hematuria, fistula formation or proctitis, no additional subjects will be enrolled and the trial will be closed. If the first subject enrolled at 75 Gy experiences Grade 4 or higher hematuria, fistula formation or proctitis, no additional subjects will be enrolled at 75 Gy and 60 Gy will be considered the MTD. Grade 4 hematuria is defined as hematuria with life-threatening consequences and urgent radiologic or operative intervention indicated. Grade 4 or higher fistula (anal or urinary) formation is defined as a fistula with life-threatening consequences with urgent radiologic or operative intervention indicated. Grade 4 or higher proctitis is defined as proctitis with life-threatening consequences and urgent intervention indicated. The time frame for DLT evaluation is the first 90 days after EBRT. EBRT is given 6 weeks after RP+ Civasheet implant at 45 Gy in 25 fractions (Monday-Friday for 5 weeks). If > 33 % of subjects experience DLT at any dose level, the dose level below that level will be

considered the MTD. Or if the highest level (75 Gy) has been reached and < 33% of subjects have experienced DLT, 75 Gy will be considered the MTD. If in the first subject treated at 75 Gy, NCI-CTCAE Grade 4 or higher hematuria, prostatitis or fistula formation occur, no additional subjects will be enrolled at 75 Gy and 60 Gy will be considered the MTD.

**Secondary:** We will describe the adverse events, toxicity and complication profile associated with Civasheet overall and at each dose when administered with RP and EBRT and also separately for those not receiving EBRT. Overall and for 60 and 75 Gy, the toxicity and complication profile associated with the Civasheet® will be assessed. Rates for surgical complications and adverse events, acute (< 90 days) and late (18 months days) GU and GI toxicity and adverse events using the NCI-CTCAE v4.0, RTOG Acute Toxicity Scale and Late Radiation Morbidity scales will be assessed. Erectile preservation and total urinary incontinence will be assessed overall and for each dose group once all subjects have completed the 6 month follow-up after EBRT. Peri- and post-operative complications associated with surgery will be assessed and graded using the Clavien-Dindo classification of surgical complications. Erectile preservation rates [IIEF score (erectile component) > 18] will be assessed, continence defined as the use of no pads will also be assessed. Binary or categorical outcomes will be described with proportion and 95% confidence intervals and continuous measures will be summarized with mean (SD) or median (IQR), as appropriate.

BCR defined as a post-prostatectomy serum PSA > 0.2 ng/ml will also be assessed for each subject. To evaluate cancer control, the Kaplan Meier-Method will be used to estimate BCR overall and for each dose group and separately for those receiving vs. not receiving EBRT once all subjects have completed the 6 months follow-up after EBRT or 6 months follow-up after Civasheet implant if no EBRT is given.

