The dose escalation design utilized for the present study will proceed as follows: The first subject will be enrolled at 60 Gy. Once the entire DLT window (i.e., 90 days post EBRT) is complete for this first subject, the next 2 subjects will be enrolled at 60 Gy. If in the first subject, grade 4 or higher hematuria, proctitis, fistula formation or death occurs in the DLT window, the trial will be terminated. If 2 of the first 3 subjects experience DLT at 60 Gy, the trial will be terminated. If 0 or 1 of the first 3 subjects enrolled at 60 Gy experience a DLT after the third subject's entire DLT window is complete, an additional three subjects will be enrolled at 60 Gy. If $\geq 33\%$ of subjects experience DLT at 60 Gy, the trial will be terminated. If after the sixth subject's DLT window is complete and < 33% of subjects experience DLT at 60 Gy, the first subject at 75 Gy will be enrolled. Once the entire DLT window (i.e., 90 days post EBRT) is complete for this first subject at 75 Gy, the next two subjects will be enrolled at 75 Gy. If in the first subject at 75 Gy, grade 4 or higher hematuria, fistula formation, proctitis or death occurs in the DLT window, 60 Gy will be considered the MTD and no additional subjects will be enrolled at 75 Gy. If 2 of the first 3 subjects experience DLT at 75 Gy, 60 Gy will be considered the MTD and no additional subjects will be enrolled at 75 Gy. If 1 or 0 of the first 3 subjects enrolled at 75 Gy experience a DLT after the third subject's entire DLT window is complete, an additional 3 subjects will be enrolled at 75 Gy. If $\geq 33\%$ of subjects experience DLT at 75 Gy, no additional subjects will be enrolled at 75 Gy and 60 Gy will be considered the MTD. If after the sixth subject's DLT window is complete and < 33% of subjects experience DLT at 75 Gy, 75 Gy will be considered the MTD.

The true risk of toxicity is expected to be in the range of 10-50%. The following table shows the corresponding probabilities of dose escalation.

True Risk of Toxicity	0.1	0.2	0.3	0.4	0.5
Probability of Escalation	0.96	0.87	0.69	0.50	0.31

[Type here]

Protocol Title:	A Phase I Single-Arm Open Label Dose-Escalation Study of CivaSheet with Radical Prostatectomy with or without Adjuvant External Beam Radiation Therapy in Patients with High Risk Prostate Cancer
Principal Investigator Name/Contact Info:	[name]/ [contact]/ [contact]
Primary Contact Name/Contact Info	[contact] [name]
Date Revised:	7/22/2022

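### The SAP clause naming 75 Gy the MTD sets no minimum number of subjects and no dose level for its 33%, and the Protocol does not settle the gap consistently

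*SAP*

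**What the plan says.** **SAP, Primary Outcome.** The rule for the top dose is "if the highest level (75 Gy) has been reached and < 33% of subjects have experienced DLT, 75 Gy will be considered the MTD", and it is repeated near the end of the same section. The sentence just before it does carry a dose level: "if > 33 % of subjects experience DLT at any dose level, the dose level below that level will be considered the MTD". The SAP gives no cohort size anywhere.

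**Protocol, section 3(c) Number of Subjects.** "If 1 or 0 of the first 3 subjects enrolled at 75 Gy experience a DLT", then "an additional 3 subjects will be enrolled at 75 Gy". The declaration of 75 Gy as MTD is conditioned as follows: "If after the sixth subject's DLT window is complete and < 33% of subjects experience DLT at 75 Gy". At 33% or more, the text is "of subjects experience DLT at 75 Gy, no additional subjects will be enrolled at 75 Gy and 60 Gy will be considered the MTD".

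**Protocol, safety-monitoring text before the Adverse Events heading.** After the first three subjects at 75 Gy the team will "enroll 3 additional subjects at 75 Gy if DLT has been observed in 1 subject, or terminate the trial", the latter at 33% or more among those three. No action is stated for 0 of 3 at 75 Gy. At 60 Gy, this text goes straight to 75 Gy after 0 of 3, whereas section 3(c) enrols three more at 60 Gy.

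**The concern.** This is the decision rule for the primary outcome. Section 3(c) attaches two conditions to naming 75 Gy the MTD: six subjects with completed windows, and a proportion taken at that dose. The SAP clause carries neither. A reader with the SAP alone could declare 75 Gy on three men without a DLT, while a reader of section 3(c) would have to treat three more first. The monitoring text does not supply the missing step. Two people could each follow a document faithfully and report different MTDs, or report the same MTD on very different evidence.

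**Working it through.** **Inputs.** The rules are those set out above. The range of true DLT risk, p = 0.1 to 0.5, and the escalation probabilities come from Protocol section 3(c). Subjects are treated as independent with a common risk at a given dose.

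**1. The plan's own figure.** Section 3(c) states escalation probabilities of 0.96, 0.87, 0.69, 0.50 and 0.31 at p = 0.1 to 0.5.

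- Its written rule (at most 1/3, always expand, then below 33% of six, so at most 1/6) gives (1−p)^6 + 6p(1−p)^5 = 0.886, 0.655, 0.420, 0.233, 0.109. This does not reproduce the table.
- Passing on 0/3, or on 1/3 expanded to at most 2/6, gives (1−p)^3 + 3p(1−p)^2 × [(1−p)^3 + 3p(1−p)^2] = 0.965, 0.856, 0.689, 0.496, 0.313. All five are within two points of the table.
- Always expanding and accepting at most 2/6 gives 0.965, 0.852, 0.680, 0.482, 0.297, also within two points.

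Of the rules tried, only those that accept 2/6 fit the table. The table therefore cannot show that the written six-subject rule is the one intended.

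**2. 0 of 3 at 75 Gy.** 0/3 = 0% is below 33%, so the SAP clause is met. Section 3(c) enrols three more. Its decision would then turn to 60 Gy if at least 2 of those three had a DLT, since 2/6 = 33.3% is at least 33%. That chance is 3p²(1−p) + p³:

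- p = 0.3: 0.189 + 0.027 = 0.216
- p = 0.4: 0.288 + 0.064 = 0.352
- p = 0.5: 0.375 + 0.125 = 0.500

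At p = 0.1 and 0.2 it is 0.028 and 0.104.

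**3. Precision.** With no events in n subjects, the upper end of the exact two-sided 95% interval is 1 − 0.025^(1/n). This is 0.708 for n = 3 and 0.459 for n = 6.

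**4. Acceptance of 75 Gy once it is reached.**

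| Reading | p = 0.3 | p = 0.4 | p = 0.5 |
|---|---|---|---|
| Section 3(c): at most 1/6 | 0.420 | 0.233 | 0.109 |
| Accept at 0/3; expand 1/3, accept 1/6: (1−p)^3 + 3p(1−p)^5 | 0.494 | 0.309 | 0.172 |
| Accept at 0/3; 1/3 = 33.3% ends the dose: (1−p)^3 | 0.343 | 0.216 | 0.125 |

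The last two rows both come from the monitoring text combined with the SAP clause. That text expands on 1 of 3 and terminates at 33% or more of three, and 1/3 is 33.3%.

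**5. Denominator.** Suppose 0/6 at 60 Gy and 2/6 at 75 Gy. Over all subjects the proportion is 2/12 = 16.7%, which satisfies the SAP clause read literally. At 75 Gy alone it is 33.3%, which exceeds 33% and triggers the preceding SAP sentence, giving 60 Gy. If 33% is shorthand for one third, 2/6 taken at 75 Gy is neither above nor below it, and neither SAP sentence assigns an MTD.

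**The case against.** The strongest reply is that section 3(c) is the full escalation algorithm and closes the gap: it expands on 0 of 3 at 75 Gy in so many words. The monitoring text is only silent there, silence is not contradiction, and it goes on to mention a next group of three at 75 Gy. This stands to the extent that the Protocol read as a whole cannot be said to declare 75 Gy on three men. It does not remove the problem. Neither document says which prevails, the SAP is where the MTD is formally defined, and the monitoring text already departs from section 3(c) on 0 of 3 at 60 Gy. It cannot be assumed to follow section 3(c) silently at 75 Gy.

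Two stronger readings are tempting. The first is that the SAP wording makes acceptance of a toxic 75 Gy more likely, for example 31% instead of 23% at p = 0.4. That holds only if 1/3 is exempted from a literal 33% threshold. If it is not, acceptance is 22% at p = 0.4 and falls from 42% to 34% at p = 0.3. The documents do not fix the direction.

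The second is that the plan pools both doses. The preceding SAP sentence is per dose level, the clause itself names 75 Gy, and section 3(c) puts the dose on the proportion. Per-dose is the natural reading. Any frequency attached to pooling would rest on assumed risks at both doses and would not be a rate of wrong MTDs.

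**Conclusion.** The point holds as a defect in the primary-outcome rule: the documents do not yield one decision rule for declaring 75 Gy. The main gap is the missing minimum number of subjects. Its size is best expressed by the reversal chance after 0/3 (22% to 50% for p between 0.3 and 0.5, under 11% for p of 0.2 or less) and by the upper limit of 71% instead of 46%. The reversal chances assume independent subjects with a common risk and take section 3(c)'s written threshold as the comparator, without implying that it is the right one. The unqualified denominator is secondary: it needs the dose level added because a literal reading would conflict with the sentence before it. No net inflation of acceptance and no error rate from pooling is claimed.

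**What to change.** Reconcile Protocol section 3(c), the Protocol's safety-monitoring text and both statements of the clause in the SAP's Primary Outcome section into one MTD rule. It should state:

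- that the proportion is among evaluable subjects at 75 Gy;
- how many must complete the DLT window before 75 Gy can be declared;
- the action at 0 of 3 at 75 Gy, with the 60 Gy conflict on 0 of 3 resolved at the same time;
- how 1/3 and 2/6 (both 33.3%) are treated against 33%.

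Then quote the acceptance probabilities of the rule chosen, and check that the escalation table in section 3(c) follows from it. Which cohort size and threshold to adopt is for the study team. The cost is a few clauses and, at most, three more men at 75 Gy than the three-subject reading, within the stated maximum of 12.
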